For additional details, see topic "Recruitment of Subjects/Advertising" on ORI's [IRB Survival Handbook web page](#) and the [PI Guide to Identification and Recruitment of Human Subjects for Research \[PDF\]](#).

The PI will share responsibility for recruitment and enrollment (i.e., attainment of written informed consent) of eligible cancer survivors with the co-investigators and research assistants (RAs) who are authorized to obtain consent. Recruitment for this study involves three separate avenues: 1) a population-based approach, 2) a clinic-based approach, and 3) an individual approach. Advertising will not be performed. Population-Based: Kentucky Cancer Registry (KCR) will assist in recruitment to the extent that its staff will identify potential participants for this study. Potentially eligible cancer survivors from the perspective of the KCR will be defined as individuals who were: 1) diagnosed with cervical or head/neck cancer (e.g., larynx, oral cavity) in the past 5 years, 2) residents of a rural or Appalachian Kentucky county at the time of cancer diagnosis, 3) between 18 and 75 years old at time of cancer diagnosis, and 4) noted as having a history of tobacco use. All of these qualities are coded in KCR's database in a manner that easily allows for the identification of potential study participants for the purposes of recruitment. KCR will make initial contact with potentially eligible individuals using their established two-step procedure. Step one involves physician notification. Specifically, KCR will contact the physician of record, inform the physician of the study and the cancer survivor's potential for study participation, and then ask the physician to inform KCR if there is any reason why the cancer survivor should not be invited to participate in the study. If the physician of record indicates the cancer survivor should not be contacted, the cancer survivor will not be invited to participate in the study. All others will advance to the next step. Step two involves cancer survivor notification. Specifically, KCR will contact cancer survivors by mail to inform them of their potential for study participation. Cancer survivors will be provided a pre-addressed, postage-paid response card on which they may indicate if they do or do not want their name and contact information released to the PI. If a reply is not received within two weeks, then up to five phone calls will be made in an attempt to obtain verbal consent for the release of the cancer survivor's name and contact information. Only those cancer survivors who "opt in" to the potential for study participation will have their names and contact information (i.e., phone number and mailing address) released to the PI. Once the PI has the names and contact information (i.e., phone number and address) of people who express interest in study participation, RAs will attempt to call these individuals and screen them for eligibility. Up to five calls will be made to each person. If someone cannot be reached by phone, then 1-2 introductory letters will be mailed to the address of record (see attachment in the "Research Procedures" section). These letters will contain office phone numbers that interested individuals can use to contact the PI or RAs. Over the phone (whether the call is initiated by the research team or the cancer survivor), cancer survivors will be given a brief overview of the study procedures, have their initial questions answered, and screened for eligibility (see attachment in the "Research Procedures" section). If interested and eligible, attempts will then be made to enroll them into the study (see "Informed Consent Process" below). A few notes about the KCR: First, its recruitment procedures are not subject to modification by an individual investigator and a standardized postcard is used for notification about potential study participation; this is outside the PI's control. Second, it is not part of a "covered entity" and therefore HIPAA authorization for release of Personal Health Information, including contact information, is not required. Finally, study personnel will not have access to any identifying information for any cancer survivor until the standardized recruitment procedures described below are complete. Clinic-Based: Clinic-based recruitment focuses on recently diagnosed cancer survivors because they are unlikely to be captured in KCR's database due to the lag time between cancer diagnosis and registry entry. Here participants will be recruited through Markey Cancer Center's 1) Multidisciplinary Clinic and 2) Gynecological Oncology Clinic. On a weekly basis, [name] (Multidisciplinary Clinic – head/neck cancer care), [name] [name] (Gynecological Oncology Clinic – cervical cancer care), and/or RAs will access the UK HealthCare's electronic health record system in use in the Markey Cancer Center to review the relevant clinic schedules and identify patients presenting for an appointment related to a head/neck or cervical cancer diagnosis that occurred in the past year. If patients' healthcare provider agrees, then the PI or a RA will speak with the patient that day about the study (schedule permitting). As per the norm for the aforesaid clinics, an exam room or other private room will be used to give patients a brief overview of the study procedures and then screen them for eligibility. If interested and eligible, attempts will then be made to enroll patients into the study. If an in-person conversation is not possible the day of patients' appointment due to incompatible schedules or whatever else, then a RA will follow-up with that individual via phone within a couple of weeks. In this scenario, the same approach that is used to reach potential participants identified by KCR will be used (i.e., phone call(s) then letter(s)). Again, if individuals are found to be interested and eligible, attempts will then be made to enroll them into the study. In order to carryout this aspect of recruitment, we need to generate a list of individuals to be screened for eligibility (i.e., a list of individuals who are scheduled for an appointment related to a recent (i.e., past year) head/neck or cervical cancer diagnosis). This list will contain only this info: patients' first and last name, address, phone number, and appointment info (i.e., place, date, and time); no other PHI is needed for these individuals. This information is necessary in order to 1) have the RAs arrange their schedule so they can try to screen people in person and 2) have the RAs follow-up with someone missed in clinic. A HIPAA Waiver of Authorization is requested for this aspect of the study. Individuals: Cervical and head/neck cancer survivors in the PI's active studies (IRB #14-0599-P4S and 16-0517-P4S) who on their Consent Form answered "yes" to the question about being contacted for future studies will be contacted about this study. Once again, the same approach that is used to reach potential participants identified by KCR will be used (i.e., phone call(s) then letter(s)). And again, if individuals are found to be interested and eligible, attempts will then be made to enroll them into the study. Regardless of the avenue by which people are recruited, each individual identified as a potential participant will be assigned a unique identification number (e.g., 568, 254), and there will exist an electronic document that links each individual's name and contact info (address, and phone numbers) with their unique identification number.

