Data for this study comes from one of two sources: 1) KCR and 2) surveys. All data collected for this study are required in order to meet the specific aims (see "Objectives"), or describe the study sample whenever the findings are disseminated. Once the PI obtains approval from KCR regarding the conduct of this study, KCR will provide this information about each participant: date of cancer diagnosis, age at cancer diagnosis, site of cancer at diagnosis, stage of cancer at diagnosis, type of cancer treatment, date of initiation and completion of cancer treatment, and insurance coverage at cancer diagnosis. For the surveys, standardized measures and individual questions commonly used in cancer survivorship, quality of life, and/or tobacco use research will be asked. Permission is not needed to use any of the measures listed below as they are all either developed by the PI or in the public domain. The baseline (Day 0) and follow-up (Day 30 and 60) surveys contain similar measures, but the baseline is longer than the follow-up and some modifications to individual items were made as appropriate; see Data Collection attachment for more information. No information will be entered into participants' EHR as part of this study.

Confidentiality: Specify where the data and/or specimens will be stored and how the researcher will ensure the privacy and confidentiality of both. Please address the following items or indicate if the following has been addressed in a HIPAA or Limited Review form:

- physical security measures (e.g., locked facility, limited access);
- data security (e.g., password-protection, data encryption);
- who will have access to the data/specimens and identifiers;
- safeguards to protect identifiable research information (e.g., coding, links, certificate of confidentiality);
- procedures employed when sharing material or data, (e.g., honest broker if applicable, written agreement with recipient not to re-identify, measures to ensure that subject identifiers are not shared with recipients).
- management after the study

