1. Accrual will be calculated as the number of participants enrolled divided by the number of individuals contacted about study participation. It will be reported as a percentage. No inferential statistical test will be conducted for this outcome. Only descriptive analyses apply.
2. Retention will be calculated as the number of assessments at the end of study divided by the number of participants enrolled. It will be reported as a percentage. No inferential statistical test will be conducted for this outcome. Only descriptive analyses apply.
3. Acceptability will be determined by the total score on the Treatment Acceptability and Preferences measure. It will be reported as a mean. An Independent samples t-test (2 sided) will be used to examine if the treatment group reports a better outcome than the control group.

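### Does the accrual rate need a defined contact event, given that the registry makes the first approach and the study team sees only those who opt in?

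*Combined protocol and SAP*

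**What the plan says.** SAP, Outcome Measures, item 1: "Accrual will be calculated as the number of participants enrolled divided by the number of individuals contacted about study participation". The result is a percentage, reported descriptively and without an inferential test. Under Study Design, accrual and retention are the two feasibility outcomes of the pilot, and the enrolment goal is 80.

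Subject Recruitment Methods & Privacy describes three routes.

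- **Registry.** KCR first notifies the physician of record. If the physician objects, "the cancer survivor will not be invited to participate in the study". Otherwise, "KCR will contact cancer survivors by mail to inform them of their potential for study participation". People who do not reply get up to five calls from KCR. Only those who agree have their details passed on, after which the study team makes up to five calls and may send one or two letters. The section adds that "study personnel will not have access to any identifying information for any cancer survivor until the standardized recruitment procedures described below are complete", and says of KCR that "its recruitment procedures are not subject to modification by an individual investigator".
- **Clinic.** If the patient's "healthcare provider agrees, then the PI or a RA will speak with the patient that day about the study"; a patient missed that day is followed up by phone and then letter.
- **Prior studies.** Survivors who had agreed to hear about future research are called or written to by the team.

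Research Materials, Records and Privacy says: "Data for this study comes from one of two sources: 1) KCR and 2) surveys". It introduces the registry items with "KCR will provide this information about each participant" and then lists clinical and insurance fields.

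**The concern.** Several registry events could count as contact: KCR's letter, KCR's calls, release of the name, the study team's call or letter, or a conversation actually held. Each gives a different denominator. First outreach is the most literal reading, but KCR performs it, and no mailing count appears among the listed data. The figure closest to hand is the number of names released, which already leaves out people who refused or never answered.

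The two figures answer different questions. Counting from the mailing describes reach into the registry population; counting from released names describes uptake among people who had already agreed to be approached. Recruitment is said to lean on the registry, and feasibility is a main purpose of the pilot. A reader who took the second figure for the first would be too optimistic about reach.

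**Working it through.** **Is there a figure to reproduce?** No. The documents give no expected accrual percentage, mailing count, opt-in rate or feasibility threshold.

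**Direction.** Let E be the number enrolled, M the number mailed by KCR, N the names released and O the people first contacted by the team on the other two routes.

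- Accrual from the mailing = E/(M + O)
- Accrual from names = E/(N + O)

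Released names are a subset of those mailed, so N ≤ M and the second figure is never smaller. They are equal only if everyone mailed opts in.

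**Size.** Write p = N/M for the opt-in share and s = N/(N + O) for the registry share of the team's contacts. Then

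ratio = (N/p + O)/(N + O) = s/p + (1 − s),

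which cannot exceed 1/p. E cancels. The values of p and s below are assumptions.

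| s | p = 80% | p = 50% | p = 20% |
|---|---|---|---|
| 50% | 0.625 + 0.5 = 1.125 | 1.0 + 0.5 = 1.50 | 2.5 + 0.5 = 3.00 |
| 90% | 1.125 + 0.1 = 1.225 | 1.8 + 0.1 = 1.90 | 4.5 + 0.1 = 4.60 |
| 100% | 1.25 | 2.00 | 5.00 |

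Worked case with E = 80 and assumed N = 300, O = 100, p = 50%: from names, 80/400 = 20.0%; from the mailing, 80/(600 + 100) = 11.4%; ratio 1.75 = 0.75/0.5 + 0.25. The formula assumes that nobody appears on two routes, which the protocol does not rule out.

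**Does the text leave the choice open?** Less than item 1 alone suggests. The recruitment section describes KCR as making the initial contact, and its sentence on the mailing, "KCR will contact cancer survivors by mail to inform them of their potential for study participation", is close to the wording of item 1. Read together, they favour the mailing as the registry event. On the clinic and prior-study routes the team makes the first contact itself, so no opt-in step intervenes.

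**Is the mailing count unobtainable?** Nothing shows that it is. The restriction is on identifying information before opt-in; an aggregate count identifies nobody. That KCR's procedures cannot be altered does not prevent KCR from reporting how many letters it sent. The list of data sources does not settle the matter either: it covers participant-level fields and mentions no recruitment tally for any route. By that test, names released and clinic approaches would be missing too.

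**What depends on the figure?** No hypothesis test, success criterion or sample size uses it. Either denominator gives a valid descriptive yield once it is named.

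**The case for a change.** The strongest case for a change is that accrual is one of only two feasibility outcomes and that the undefined term has a known direction of drift. An analyst who takes the convenient count will report the higher number. Leaving the choice until after recruitment lets it be made with the results in view, while two sentences in the SAP would close it off. Names and contact details of people who do not enrol are kept only to 07/31/20, so a late decision could find the records gone.

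The gap and its direction stand. The rest carries less weight. With no threshold to clear, a favourable choice of denominator wins nothing, and it is visible as soon as the denominator is printed. Enrolment is due to end on 07/31/19, a year before the retention date, and that rule covers personal details, not tallies. The 07/31/20 date also differs from the project end date of 7/31/2022, but that is a separate clerical matter.

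Fixing the definition is also less clean than it looks. A fallback to released names would pool a post-opt-in registry count with a first-approach clinic count. Calling that total accrual among survivors who had agreed to contact would be wrong for clinic patients, who are approached from appointment schedules with no prior opt-in. There is also a fair argument for counting from the team's own contact, because the study is first explained in detail at that point and KCR's process is outside the investigator's control.

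**Conclusion.** No change to the plan is called for. Item 1 leaves a term undefined, but the protocol's recruitment section already points to KCR's mailing as the registry contact. The outcome is descriptive and no decision rule rests on it. An analyst would ordinarily state the denominator with the percentage and, where counts allow, show the routes separately; if only released names were available, the registry figure alone would be described as uptake among those who agreed to release their details.

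The difference between the two readings is a factor of s/p + (1 − s). It is 1 if everyone mailed opts in and at most 1/p otherwise. The values from 1.13 to 5.00 rest entirely on assumed opt-in and registry shares and are not estimates for this trial. The conclusion rests on the text available; the grant application and eligibility screener are attached to the protocol but not reproduced in it, and either may define contact.

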This is a pilot (Phase II) randomized clinical trial with randomization in a 1:1 ratio. The control group will receive a brief consultation (10-15 minutes via phone) about free or low-cost resources that may help them address unmet social support needs. Additionally, a written directory of a range of social support resources will be delivered via mail. The treatment group will receive the aforesaid intervention plus brief advice to quit smoking (10-15 minutes via phone). Additionally, a written summary of the benefits of smoking cessation, evidence-based approaches to quit, and the basics of NRT in addition to a free, 2-week supply of nicotine patches and lozenges will be delivered via mail. As a pilot, this study focuses on the outcomes of feasibility (i.e., accrual and retention) and acceptability (e.g., participants' perceptions of appropriateness and effectiveness) as opposed to efficacy (though this is also important). Despite the use of an intervention, participants in this study are not "treatment seeking" smokers and the study will not be advertised as an "intervention" or "treatment" for smokers who want to quit. This is because the goal is to encourage the occurrence of quit attempts among smokers who may or may not be interested in smoking cessation in the near future as opposed to promotion of sustained abstinence among smokers who express readiness to quit. The emphasis on smoking cessation induction (that is, the inducement or promotion of a quit attempt) is an important aspect of the study design and is appropriate for smokers across the continuum of motivation to quit. Given the focus on "all comers" with respect to motivation to quit, the behavioral target of quit attempts instead of prolonged abstinence, and a minimal intervention (specifically, a 2-week supply of NRT), the period of follow-up is relatively brief (Day 0 to Day 60, or 2 months). All of the intervention components will be delivered remotely via mail or phone in order to test this intervention in the "real world" where it would be difficult for cancer survivors to travel far for smoking cessation treatment. Finally, it is important to note that biochemical verification of self-reported quit attempts will not occur (see "Alternative Methods" section of the grant for more the rationale). The anticipated start and end of enrollment is 10/01/17 and 07/31/19, respectively. The goal is to enroll 80 cervical and head/neck cancer survivors who at the time of enrollment are within 5 years from the date of cancer diagnosis. In the absence of any preliminary data, it is unknown how the final sample will be split in terms of cervical versus head/neck cancer survivors. The eligibility criteria (see Study Population) were selected to balance the needs of the study with the desire to increase generalizability of study findings to cancer survivors who are at high risk for persistent smoking (i.e., tobacco-related cancer survivors who were smokers at or near the time of cancer diagnosis; [name] et al., 2015). During the course of study participation, participants' health status may vary as a result of living with cancer and any other chronic disease. Nonetheless, this study is not expected to engender more than minimal risk to participants' physical health, as the anticipated adverse events (AE) are most likely to be mild or moderate in severity and short-term in duration (see "Potential Risks").

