The overall risks to participants are low in terms of both their likelihood and seriousness. The physical risks associated with use of nicotine patch and/or nicotine lozenge in this study are expected to be rare and mild. In prior studies of NRT (many of which have much longer sampling periods), adverse events were documented to occur in the majority of participants (~70%), but dropout due to AEs was low (~7%) and the report of serious AEs was even lower (~2%) (e.g., Carpenter et al., 2011; Jardin et al., 2014). The most common AEs for the NRT under study here are skin irritation (patch), headache (patch), insomnia (patch), mouth and throat soreness (lozenge), hiccups (lozenge), and nausea (patch and lozenge) (Hughes et al., 2004; Mills et al., 2010; Piper et al., 2011). It should be appreciated that concurrent use of cigarettes and NRT, which rarely occurs (Shiffman, Hughes, DiMarino, & Sweeney, 2003), is now considered to be safe (Fagerstrom & Hughes, 2002) despite the risk for nicotine "overdose" or "intoxication" as characterized by nausea, vomiting, dizziness, diarrhea, weakness, and rapid heartbeat. Therefore, the FDA now suggests that it is unnecessary to quit smoking before starting NRT and it is unnecessary to stop NRT if lapse or relapse to smoking occurs. The psychological risks are those associated with being asked questions about the following: 1) demographics, including access to health care, 2) cancer survivorship, 3) quality of life, 4) tobacco use and cessation, and 5) social environment/relationships. Although completion of the surveys might result in mild emotional discomfort, based on the PI's experience, the likelihood of psychological risk is low and the severity of this risk is mild. Furthermore, participants always have the option of not completing a survey or skipping an item. It should be noted that the extant data on NRT sampling (as opposed to provision or recommendation of a full, standard dose of NRT) does not suggest that it undermines smoking cessation, thus reductions in motivation, confidence, and behavior change are considered to be very low in likelihood and severity. There are confidentiality risks. The health-related and other private information obtained from KCR, EHR, and participants is considered sensitive in nature, and a breach of confidentiality for these data could pose a mild to moderate risk to participants. Since especially sensitive information regarding sexual orientation, criminal history, or a history of treatment for substance abuse/dependence (other than treatment for nicotine dependence) will not be collected for this study, the consequence of an individual's survey responses being revealed is thought to be mild. However, to minimize any adverse consequences of a breach of confidentiality for these data, solely participants' unique identification number will identify all survey data. The financial risks are the costs associated with regular use and maintenance of a landline or cellular phone. These risks are likely to be of little consequence, given that no one is required to modify their pre-existing phone access as part of study procedures. Finally, it should be noted that mailing NRT is a very well-accepted method to disseminate NRT (Carpenter et al., 2011 Archives of Internal Medicine; Cunningham et al., 2016 JAMA Internal Medicine; Kushner et al., 2017 Addictive Behaviors; Jardin et al., 2014 Nicotine and Tobacco Research; Solomon, Scharoun, Flynn, Secker-Walker, & Sepinwall, 2000 Preventive Medicine; Zawertailo et al., 2012 Tobacco Control). This is standard practice for state Quitlines, and like the Quitlines, NRT will be mailed to participants sans tracking or signature confirmation, both of which add unnecessary cost and burden to the procedures and participants alike. The approach proposed here is considered acceptable for several reasons, including largely NRT's over-the-counter status, relatively benign adverse event profile, and low abuse liability (West et al., 2000; Psychopharmacology) coupled with the fact that the treatment group in this study actually gains access to an evidence-based treatment for smoking cessation as part of study participation.

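### The acceptability comparison leaves out cancer site, a baseline factor already on file; using it would give modest precision and a by-site description, although the planned t-test is valid

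*Combined protocol and SAP*

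**What the plan says.** The SAP, Outcome Measures, lists three outcomes. Accrual and retention are descriptive only. Acceptability is the one outcome with a test: "Acceptability will be determined by the total score on the Treatment Acceptability and Preferences measure", it is reported as a mean, and "An Independent samples t-test (2 sided) will be used to examine if the treatment group reports a better outcome than the control group". Alpha, SD, target difference and power are not given. No covariate, stratum or by-site table is named.

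Under Study Design, "This is a pilot (Phase II) randomized clinical trial with randomization in a 1:1 ratio", and "The goal is to enroll 80 cervical and head/neck cancer survivors". The same section says that "it is unknown how the final sample will be split in terms of cervical versus head/neck cancer survivors", and names feasibility and acceptability as the pilot's focus.

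Other relevant places in the protocol:

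- **Subject Recruitment Methods:** head/neck cancer includes larynx and oral cavity, and all three recruitment routes select people by cancer site.
- **Research Procedures:** only the arm given nicotine replacement therapy (NRT) is sent patches and lozenges, and participants may decline the shipment. Randomisation follows a biostatistician's protocol that is not described.
- **Potential Risks:** soreness of the mouth and throat is listed among the common effects of the lozenge.
- **Research Materials, Records and Privacy:** the registry supplies "site of cancer at diagnosis" for each participant.

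**The concern.** Two clinically different groups are combined, and the one planned test takes no account of which group a participant belongs to. Site could matter in two separate ways.

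1. **As a predictor of the score in both arms.** Cervical survivors are all women, head/neck survivors are of both sexes, and disease and treatment differ. If site predicts the score, leaving it out wastes some precision. It also leaves the single realised comparison exposed to a chance difference in site mix between arms.
2. **As a modifier of the arm difference.** Only one arm is sent a product with oral side effects, and some participants have had cancer of the mouth or throat. If the package suits one group less well, the pooled difference is an average that depends on the recruited mix, and nothing in SAP item 3 would show it.

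At stake is how useful the acceptability result is for designing the next trial. The correctness of the test is not in question.

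**Working it through.** **Inputs from the documents.** N = 80 at 1:1, so 40 per arm. The enrolment table under Subject Demographics gives 24 men and 56 women. Men must be head/neck survivors, so if that target is met the head/neck share is at least 24/80 = 30%. Study Population expects relatively higher enrolment of cervical survivors, which argues against a head/neck majority. The range used for the share p is therefore 30-50%.

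**Assumptions.** The documents give no SD and no site effect. Assumed: a site effect d of 0.5 or 0.8 within-site SD, alpha 0.05 two-sided, and allocation not stratified by site. The plan states no figure of its own to reproduce.

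**1. Validity.** In 20,000 simulated trials per scenario (p = 30% or 50%, d = 0.5 or 0.8, no treatment effect), the unadjusted t-test rejected in 4.9-5.1%. Overall type I error is correct.

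**2. Precision if site shifts the score equally in both arms.** Ratio of adjusted to unadjusted standard error = 1/sqrt(1 + p(1-p)d²).

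| p | d | p(1-p)d² | Ratio | Reduction |
|---|---|---|---|---|
| 30% | 0.5 | 0.0525 | 0.975 | 2.5% |
| 50% | 0.5 | 0.0625 | 0.970 | 3.0% |
| 30% | 0.8 | 0.1344 | 0.939 | 6.1% |
| 50% | 0.8 | 0.1600 | 0.928 | 7.2% |

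This takes the arms as balanced on site. Chance imbalance gives a little back: the mean squared correlation of arm with site is 1/(80-1) = 0.0127, so the standard error rises by about 1/sqrt(1-0.0127) = 1.006, or 0.6%. Power for an assumed true difference of 0.5 SD goes from 0.58-0.59 to 0.61 (d = 0.5) and from about 0.55 to 0.61 (d = 0.8).

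**3. Precision if site matters only in the arm sent lozenges.** Average variance is 1 + p(1-p)d²/2 unadjusted. With a common site term it is 1 + p(1-p)d²/4, because the term fits half the effect in each arm. The ratio is sqrt(1.0131/1.0263) = 0.994 at p = 30%, d = 0.5, and sqrt(1.04/1.08) = 0.981 at p = 50%, d = 0.8. The reduction is 0.6-1.9%, before the 0.6% given back.

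**4. Chance imbalance.** Hypergeometric: 80 people, 80p of them head/neck, 40 drawn to one arm.

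| Gap in head/neck share | Probability, p = 30% | Probability, p = 50% | Shift = gap × d |
|---|---|---|---|
| at least 10 points | 0.465 | 0.503 | 0.05-0.08 SD at 10 points |
| at least 15 points | 0.222 | 0.263 | 0.075-0.12 SD at 15 points |
| at least 20 points | 0.087 | 0.117 | 0.10-0.16 SD at 20 points |

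The standard error of the arm difference is sqrt(2/40) = 0.22 SD, so a 15-point gap moves the estimate by about a third to a half of one standard error. In the simulated trials with a gap of 20 points or more, the t-test rejected in about 7% (d = 0.5) and 10% (d = 0.8).

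**5. Effect modification.** Suppose the package raises the score by 0.5 SD in cervical survivors and by 0 in head/neck survivors. The pooled difference is 0.5(1-p): 0.35 SD at 30% and 0.25 SD at 50%. A model with arm and site returns essentially the same average. An interaction test for a 0.5 SD difference has standard error sqrt(2/12 + 2/28) = 0.49 at p = 30% and sqrt(2/20 + 2/20) = 0.45 at p = 50%, hence power of only about 18-20%. Description by site is the most that 80 people can support: at p = 30% there are 12 head/neck survivors per arm, and a 95% interval for the arm difference among them has half-width 1.96 × sqrt(2/12) = 0.80 SD.

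**The case against.** A reader might infer that the t-test is biased, or that site imbalance makes its result invalid. The documents do not support that. Arms are randomised, and the t-test's standard error already allows for chance imbalance in any baseline factor. This stands in full.

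A reader might also infer that arms will often be badly unbalanced. The probabilities above apply only to allocation not stratified by site. The allocation protocol is not shown, so stratification is neither stated nor excluded. If allocation is stratified, imbalance is largely prevented. The site term would still be apt, because the t-test would otherwise ignore the stratification factor.

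A third tempting reading is that adjustment would correct for the lozenge being less acceptable to head/neck survivors. It would not: that is a treatment-by-site difference, and only the by-site description speaks to it. The clinical link is also an inference. The protocol lists oral soreness as a general lozenge effect and ties it to no cancer site. Participants may decline the shipment, and the package also contains advice, consultation, a directory and patches.

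Finally, this is a small pilot, and baseline motivation or nicotine dependence might predict the score as well as site does. That is fair. Site has the particular claim that it is the line along which the eligible population is pooled, and the protocol itself says the mix is unknown.

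**Conclusion.** A minor, nearly free improvement to SAP item 3. The planned test is unbiased with correct overall type I error. Adding site would make the standard error about 2.5-7% smaller if site shifts the score by 0.5-0.8 SD in both arms, and less than 2% smaller if it matters only in the arm sent lozenges. It would also protect the one realised comparison against an unlucky draw, if allocation is not stratified by site. The site effects are assumptions without support in the documents; if site does not predict the score, nothing is gained. The separate gap is that a single pooled comparison, adjusted or not, cannot show whether acceptability of the package differs between the two groups. A descriptive by-site table would let the pilot look at that without claiming to test it.

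**What to change.** In SAP item 3:

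- Replace the t-test with a linear model for the acceptability total score containing arm and cancer site (cervical or head/neck). Report the adjusted difference between arms with its 95% interval.
- Add a table of the acceptability mean, SD and n by arm within each site. Label it descriptive, with no test by site.

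The cost is SAP wording and one degree of freedom (residual 77 instead of 78 with all 80 scored). No new data are needed. The by-site means will be imprecise, above all for head/neck survivors if they are near 12 per arm, and the text should say so. The change should be fixed before outcome data are seen, since a covariate chosen afterwards is less credible.
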